10.3.3. Definition of Cardiovascular Events

Cardiovascular Events (CV) Definition:

Investigators will be required to fill out the specific CV event page of the CRF for the following AEs and SAEs:

- Myocardial infarction/unstable angina
- Congestive heart failure
- Arrhythmias
- Valvulopathy
- Pulmonary hypertension
- Cerebrovascular events/stroke and transient ischemic attack
- Peripheral arterial thromboembolism
- Deep venous thrombosis/pulmonary embolism
- Revascularization

10.3.4. Recording and Follow-Up of AE and SAE

AE and SAE Recording

- When an AE/SAE occurs, it is the responsibility of the investigator to review all documentation (e.g., hospital progress notes, laboratory, and diagnostics reports) related to the event.
- The investigator will then record all relevant AE/SAE information.
- It is **not** acceptable for the investigator to send photocopies of the participant's medical records to GSK in lieu of completion of the GSK required form.
- There may be instances when copies of medical records for certain cases are requested by GSK. In this case, all participant identifiers, with the exception of the participant number, will be redacted on the copies of the medical records before submission to GSK.
- The investigator will attempt to establish a diagnosis of the event based on signs, symptoms, and/or other clinical information. Whenever possible, the diagnosis (not the individual signs/symptoms) will be documented as the AE/SAE.

Assessment of Intensity

The investigator will make an assessment of intensity for each AE and SAE reported during the study and assign it to 1 of the following categories:

- Mild: Asymptomatic or mild symptoms; clinical or diagnostic observations only; intervention not indicated.
- Moderate: Minimal, local or noninvasive intervention indicated; limiting ageappropriate instrumental Activities of Daily Living (ADL). Instrumental ADL refers to preparing meals, shopping for groceries or clothes, using the telephone, managing money, etc.
- Severe: Severe or medically significant but not immediately life-threatening; hospitalization or prolongation of hospitalization indicated; disabling, limiting self-care ADL. Self-care ADL refers to bathing, dressing and undressing, feeding self, using the toilet, taking medications, and not bedridden.

Assessment of Causality

- The investigator is obligated to assess the relationship between study intervention and each occurrence of each AE/SAE. The investigator will use clinical judgment to determine the relationship.
- A reasonable possibility of a relationship conveys that there are facts, evidence, and/or arguments to suggest a causal relationship, rather than a relationship cannot be ruled out.

- Alternative causes, such as underlying disease(s), concomitant therapy, and other risk factors, as well as the temporal relationship of the event to study intervention administration will be considered and investigated.
- The investigator will also consult the IB and/or Product Information (for marketed products), in his/her assessment.
- For each AE/SAE, the investigator must document in the medical notes that he/she has reviewed the AE/SAE and has provided an assessment of causality.
- There may be situations in which an SAE has occurred, and the investigator has minimal information to include in the initial report to GSK. However, it is very important that the investigator always make an assessment of causality for every event before the initial transmission of the SAE data to GSK.
- The investigator may change his/her opinion of causality in light of follow-up information and send an SAE follow-up report with the updated causality assessment.
- The causality assessment is one of the criteria used when determining regulatory reporting requirements.

Follow-up of AE and SAE

- The investigator is obligated to perform or arrange for the conduct of supplemental measurements and/or evaluations as medically indicated or as requested by GSK to elucidate the nature and/or causality of the AE or SAE as fully as possible. This may include additional laboratory tests or investigations, histopathological examinations, or consultation with other health care professionals.
- If a participant dies during participation in the study or during a recognized followup period, the investigator will provide GSK with a copy of any postmortem findings including histopathology.
- New or updated information will be recorded in the originally submitted documents.
- The investigator will submit any updated SAE data to GSK within 24 hours of receipt of the information.

10.3.5. Reporting of SAE to GSK

SAE Reporting to GSK via Electronic Data Collection Tool

- The primary mechanism for reporting SAE to GSK will be the electronic data collection tool.
- If the electronic system is unavailable, then the site will use the paper SAE data collection tool (see next section) to report the event within 24 hours.
- The site will enter the SAE data into the electronic system as soon as it becomes available.
- After the study is completed at a given site, the electronic data collection tool will

be taken off-line to prevent the entry of new data or changes to existing data.

- If a site receives a report of a new SAE from a study participant or receives updated data on a previously reported SAE after the electronic data collection tool has been taken off-line, then the site can report this information on a paper SAE form (see next section) or to the Medical Monitor by telephone.
- If the site during the course of the study or poststudy becomes aware of any serious, nonserious AEs, pregnancy exposure, related to any GSK product that is not part of the study design, they will report these events to GSK or to the concerned Competent Authority (CA) via the national spontaneous reporting system. These will be classified as spontaneous Individual Case Safety Reports (ICSR).
- Contacts for SAE reporting can be found in the SRM.

SAE Reporting to GSK via Paper Data Collection Tool

- Facsimile transmission of the SAE paper data collection tool is the preferred method to transmit this information to the Medical Monitor.
- In rare circumstances and in the absence of facsimile equipment, notification by telephone is acceptable with a copy of the SAE data collection tool sent by overnight mail or courier service.
- Initial notification via telephone does not replace the need for the investigator to complete and sign the SAE data collection tool within the designated reporting time frames.
- Contacts for SAE reporting can be found in the SRM.

10.4. Appendix 4: Contraceptive and Barrier Guidance

10.4.1. Definitions:

Woman of Childbearing Potential (WOCBP)

Women in the following categories are considered WOCBP (fertile):

- 1. Following menarche
- 2. From the time of menarche until becoming postmenopausal unless permanently sterile (see below)

Notes:

- A postmenopausal state is defined as no menses for 12 months without an alternative medical cause.
 - A high follicle-stimulating hormone (FSH) level in the postmenopausal range may be used to confirm a postmenopausal state in women not using hormonal contraception or hormonal replacement therapy (HRT). However, in the absence

- of 12 months of amenorrhea, confirmation with more than one FSH measurement is required.
- Females on HRT and whose menopausal status is in doubt will be required to
 use one of the non-estrogen hormonal highly effective contraception methods if
 they wish to continue their HRT during the study. Otherwise, they must
 discontinue HRT to allow confirmation of postmenopausal status before study
 enrolment.
- Permanent sterilization methods (for the purpose of this study) include:
 - Documented hysterectomy
 - Documented bilateral salpingectomy
 - Documented bilateral oophorectomy

For individuals with permanent infertility due to an alternate medical cause other than the above, (e.g., Mullerian agenesis, androgen insensitivity, gonadal dysgenesis), investigator discretion should be applied to determining study entry.

Note: Documentation can come from the site personnel's review of the participant's medical records, medical examination, or medical history interview.

If fertility is unclear (e.g., amenorrhea in adolescents or athletes) and a menstrual cycle cannot be confirmed before first dose of study intervention, additional evaluation should be considered.

Woman of Non-childbearing Potential (WONCBP)

Women in the following categories are considered WONCBP:

- 1. Premenopausal female with permanent infertility due to one of the following (for the purpose of this study):
 - Documented hysterectomy
 - Documented bilateral salpingectomy
 - Documented bilateral oophorectomy

For individuals with permanent infertility due to an alternate medical cause other than the above, (e.g., Mullerian agenesis, androgen insensitivity, gonadal dysgenesis), investigator discretion should be applied to determining study entry.

Note: Documentation can come from the site personnel's review of the participant's medical records, medical examination, or medical history interview.

- 2. Postmenopausal female A postmenopausal state is defined as no menses for 12 months without an alternative medical cause.
 - A high FSH level in the postmenopausal range may be used to confirm a
 postmenopausal state in women not using hormonal contraception or HRT.
 However, in the absence of 12 months of amenorrhea, confirmation with more
 than one FSH measurement is required.

218079

Protocol Amendment 5 Final

Females on HRT and whose menopausal status is in doubt must discontinue HRT to allow confirmation of postmenopausal status before study enrolment.

10.4.2. **Contraception Guidance:**

Female participants

Use of effective contraceptive methods will be required from at least 14 days prior to first dose and until 30 weeks after the last administered dose:

CONTRACEPTIVES^a ALLOWED DURING THE STUDY INCLUDE:

Highly Effective Methods^b That Have Low User Dependency Failure rate of <1% per year when used consistently and correctly.

- Implantable progestogen-only hormone contraception associated with inhibition of ovulation^c
- Intrauterine device (IUD)
- Intrauterine hormone-releasing system (IUS)^c
- Bilateral tubal occlusion d.
- Azoospermic partner (vasectomized or due to a medical cause) Azoospermia is a highly effective contraceptive method provided that the partner is the sole sexual partner of the WOCBP, and the absence of sperm has been confirmed. If not, an additional highly effective method of contraception should be used. Spermatogenesis cycle is approximately 90 days.

Note: documentation of azoospermia for a male participant can come from the site personnel's review of the participant's medical records, medical examination, or medical history interview.

Highly Effective Methods^b **That Are User Dependent** *Failure rate of* < 1% *per year* when used consistently and correctly.

- Combined (estrogen- and progestogen-containing) hormonal contraception associated with inhibition of ovulation^c
 - oral
 - intravaginal
 - transdermal
 - injectable
- Progestogen-only hormone contraception associated with inhibition of ovulation^c g.
 - oral
 - injectable

26 Jun 2024 125

h. Sexual abstinence

- Sexual abstinence is considered a highly effective method only if defined as refraining from heterosexual intercourse during the entire period of risk associated with the study intervention. The reliability of sexual abstinence needs to be evaluated in relation to the duration of the study and the preferred and usual lifestyle of the participant
- i. Contraceptive use by men or women should be consistent with local regulations regarding the use of contraceptive methods for those participating in clinical studies.
- j. Failure rate of <1% per year when used consistently and correctly. Typical use failure rates differ from those when used consistently and correctly.
- k. Male condoms must be used in addition to hormonal contraception. If locally required, in accordance with Clinical Trial Facilitation Group (CTFG) guidelines, acceptable contraceptive methods are limited to those which inhibit ovulation as the primary mode of action.

Note: Periodic abstinence (calendar, sympto-thermal, post-ovulation methods), withdrawal (coitus interruptus), spermicides only, and lactational amenorrhea method (LAM) are not acceptable methods of contraception for this study. Male condom and female condom should not be used together (due to risk of failure from friction)

Male participants

As depemokimab is a mAb that is not anticipated to interact directly with deoxyribonucleic acid (DNA) or other chromosomal material and minimal exposure through semen is expected, male participants will not be required to use contraception during the study.

10.5. Appendix 5: Genetics

USE/ANALYSIS OF DNA

- Genetic variation may impact a participant's response to study intervention, susceptibility, severity and progression of disease. Variable response to study intervention may be due to genetic determinants that impact drug absorption, distribution, metabolism, and excretion; mechanism of action of the drug; disease etiology; and/or molecular subtype of the disease being treated. Therefore, where local regulations and IRB/IEC allow, a blood sample will be collected for DNA analysis.
- DNA samples will be used for research related to depemokimab or CRSwNP. Genetic research may consist of the analysis of one or more candidate genes or the analysis of genetic markers throughout the genome.
- Additional analyses of DNA samples may be conducted if it is hypothesized that this may help further understand the clinical data.
- DNA samples will be analysed. Additional analyses may be conducted if it is hypothesized that this may help further understand the clinical data.

- The samples may be analyzed as part of a multi-study assessment of genetic factors involved in the response to depemokimab or study interventions of this class. The results of genetic analyses may be reported in the clinical study report or in a separate study summary.
- The sponsor will store the DNA samples in a secure storage space with adequate measures to protect confidentiality.
- The samples will be retained while research on depemokimab (or study interventions of this class) or CRSwNP continues but no longer than 15 years after the last subject last visit or other period as per local requirements.

Appendix 6: Liver Safety: Required Actions and Follow-up 10.6. **Assessments**

Liver Chemistry Stopping Criteria and Increased Monitoring Criteria are designed to assure participant safety and evaluate liver event aetiology.

10.6.1. **Liver Chemistry Stopping Criteria and Required Follow-up Assessments**

Liver Chemistry Stopping Criteria- Liver Stopping Event				
ALT Absolute	ALT ≥ 8xULN			
ALT Increase	ALT ≥ 5xULN but <8xULN persists for ≥2 weeks			
	ALT ≥ 3xULN but <5xULN persists for ≥4 weeks			
Bilirubin ^{1, 2}	ALT \geq 3xULN and total bilirubin \geq 2xULN (>35% direct bilirubin)			
INR ²	ALT ≥ 3xULN and INR>1.5			
Cannot Monitor	ALT ≥ 5xULN but <8xULN and cannot be monitored weekly for			
	≥2 weeks			
	ALT ≥ 3xULN but <5xULN and cannot be monitored weekly for			
	≥4 weeks			
Symptomatic ³	ALT ≥ 3xULN associated with symptoms (new or worsening)			
	believed to be related to liver injury or hypersensitivity			
Required Actions, Mo	onitoring and Follow up Assessments			
Actions	Follow Up Assessments			
Immediately discontinue study	Viral hepatitis serology ⁴			
intervention	Obtain INR and recheck with each liver chemistry			
Report the event to GSK within 24 hours	assessment until the aminotransferases values show			
Complete the liver event form and	downward trend			
complete SAE data collection tool if the	Obtain blood sample for pharmacokinetic (PK) analysis,			
event also meets the criteria for an SAE2	within a week of meeting increased liver monitoring			
Perform liver event follow up	criteria⁵			
assessments as described in the Follow	Obtain a Serum creatine phosphokinase (CPK) and lactate			
up Assessment column	dehydrogenase (LDH), gamma glutamyl transferase			
Monitor the participant until liver	[GGT], glutamate dehydrogenase [GLDH], and serum			

26 Jun 2024 127

Liver Chemistry Stopping Criteria- Liver Stopping Event

chemistries resolve, stabilize, or return to within baseline (see **MONITORING**)

MONITORING:

If ALT ≥3xULN AND total bilirubin ≥2xULN or INR >1.5:

- Repeat liver chemistries (include ALT, AST, alkaline phosphatase, total bilirubin, and INR) and perform liver event follow up assessments within 24 hours
- Monitor participants twice weekly until liver chemistries resolve, stabilize or return to within baseline
- A specialist or hepatology consultation is recommended

For All other criteria (total bilirubin <2xULN and INR ≤1.5):

- Repeat liver chemistries (include ALT, AST, alkaline phosphatase, total bilirubin, and INR) and perform liver event follow up assessments within 24-72 hours
- Monitor participants weekly until liver chemistries resolve, stabilize or return to within baseline

RESTART/RECHALLENGE

Do not restart/rechallenge participant with study intervention since **not allowed per protocol**; continue participant in the study for any protocol specified follow up assessments.

albumin

- Fractionate bilirubin, if total bilirubin ≥2xULN
- Obtain complete blood count with differential to assess
 eosinophilia. This blood sample will be sent to the central
 laboratory to maintain the blind while study is ongoing.
 Results will be provided only if unblinding of a participant's
 treatment assignment is required. Also note that the
 mechanism of action of depemokimab leads to lowering of
 eosinophils
- Record the appearance or worsening of clinical symptoms of liver injury, or hypersensitivity, on the liver event form
- Record use of concomitant medications on the concomitant medications report form including acetaminophen, herbal remedies, recreational drugs and other over the counter medications
- Record alcohol use on the liver event alcohol intake form

 If ALT ≥3xULN AND total bilirubin ≥2xULN or INR >1.5_obtain
 the following in addition to the assessments listed above:
- Anti-nuclear antibody, anti-smooth muscle antibody, Type 1 anti-liver kidney microsomal antibodies, and quantitative total immunoglobulin G (IgG) or gamma globulins.
- Serum acetaminophen adduct assay should be conducted (where available) to assess potential acetaminophen contribution to liver injury unless acetaminophen use is very unlikely in the preceding week. (e.g., where the participant has been resident in the clinical unit throughout).
- Liver imaging (ultrasound, magnetic resonance, or computerized tomography) to evaluate liver disease: complete Liver Imaging form.
- Liver biopsy may be considered and discussed with local specialist if available, for instance:
 - In patients when serology raises the possibility of autoimmune hepatitis (AIH)
 - In patients when suspected DILI progresses or fails to resolve on withdrawal of study intervention
 - In patients with acute or chronic atypical presentation:
- If liver biopsy conducted complete liver biopsy form.

TMF-19486952 218079

Protocol Amendment 5 Final

- Serum bilirubin fractionation should be performed if testing is available. If serum bilirubin fractionation is not immediately available, discontinue study intervention for that participant if ALT ≥3xULN and total bilirubin ≥ 2xULN. Additionally, if serum bilirubin fractionation testing is unavailable, record presence of detectable urinary bilirubin on dipstick, indicating direct bilirubin elevations and suggesting liver injury.
- All events of ALT ≥ 3xULN and bilirubin ≥ 2xULN (>35% direct bilirubin) or ALT ≥ 3xULN and INR>1.5 which may indicate severe liver injury (possible 'Hy's Law'), must be reported to GSK as an SAE; the INR threshold value stated will not apply to participants receiving anticoagulants
- 3. New or worsening symptoms believed to be related to liver injury (such as fatigue, nausea, vomiting, right upper quadrant pain or tenderness, or jaundice) or believed to be related to hypersensitivity (such as fever, rash or eosinophilia).
- 4. Includes: hepatitis A Immunoglobulin M (IgM) antibody; HbsAg and HbcAb; hepatitis C RNA; cytomegalovirus IgM antibody; Epstein-Barr viral capsid antigen IgM antibody (or if unavailable, heterophile antibody or monospot testing); and hepatitis E IgM antibody. In those with underlying chronic hepatitis B at study entry (identified by positive hepatitis B surface antigen) quantitative hepatitis B DNA and hepatitis delta antibody. If hepatitis delta antibody assay cannot be performed, it can be replaced with a polymerase chain reaction (PCR) of hepatitis D RNA virus (where needed) [Le Gal, 2005].
- 5. Record the date/time of the PK blood sample draw and the date/time of the last dose of study intervention prior to the PK blood sample draw on the CRF. If the date or time of the last dose is unclear, provide the participant's best approximation. If the date/time of the last dose cannot be approximated OR a PK sample cannot be collected in the time period indicated above, do not obtain a PK sample. Instructions for sample handling and shipping are in the central laboratory manual.

10.6.2. Liver Chemistry Increased Monitoring Criteria with Continued Study Intervention

Liver Chemistry Increased Monitoring Criteria and Actions with Continued Study Intervention Liver Monitorii Event			
Criteria	Actions		
ALT ≥ 5xULN and <8xULN and total bilirubin <2xULN or INR≤1.5 without symptoms believed to be related to liver injury or hypersensitivity, and who can be monitored weekly for 2 weeks. OR ALT ≥ 3xULN and <5xULN and total bilirubin <2xULN or INR≤1.5 without symptoms believed to be related to liver injury or hypersensitivity, and who can be monitored weekly for 4 weeks.	 learning of the abnormality to discuss participant safety. Participant can continue study intervention. Participant must return weekly for repeat liver chemistries (ALT, AST, alkaline phosphatase, total bilirubin and INR) 		

References

10.7. Appendix 7: AEs, ADEs, SAEs, SADEs, USADEs and Device Deficiencies: Definition and Procedures for Recording, Evaluating, Follow-up, and Reporting in Medical Device Studies

- The definitions and procedures detailed in this appendix are in accordance with ISO 14155 and the European Medical Device Regulation (MDR) 2017/745 for clinical device research (if applicable).
- Both the investigator and the sponsor will comply with all local medical device reporting requirements for medical devices.
- The detection and documentation procedures described in this protocol apply to all GSK medical devices provided for use in the study (see Section 6.1.1 for the list of GSK medical devices).

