Appendix Table 1 Protocol-Required Safety Laboratory Tests

Laboratory Assessments	Parameters				
Haematology ¹	Platelet Count	RBC Indices:		WBC count with Differential: (post-dose results blinded asdescribed in footnote 1)	
	RBC Count	MCV	WBC		
	Haemoglobin	MCH	Neutrophils		
	Haematocrit	%Reticulocytes	Lymphocytes		
			Monocytes		
			Eosinophils		
			Basophils		
Clinical Chemistry ²	BUN	Potassium	AST(SGOT)	Total and directbilirubin	
	Creatinine	Sodium	ALT (SGPT)	Total Protein	
	Glucose (non-fasting)	Calcium	Alkaline	Albumin	
			phosphatase ³		
		Magnesium	GGT		
Routine Urinalysis Pregnancy testing	Specific gravity pH, glucose, protein, blood, ketones by dipstick Microscopic examination and UACR (if blood or protein is abnormal[evidence of microalbuminuria or haematuria of ≥1+]) UACR will require a separate urine sample to be sent to central laboratory for analysis. Highly sensitive serum pregnancy test at Screening Visit 1, Exit Visit and at Early Withdrawal				
regnancy testing	Visit; highly sensitive urin	Visit; highly sensitive urine pregnancy tests for other assessments at time points specified in Table 1, and additionally within 24 hours prior to CT scan (as needed for WOCBP)			
Other Tests	FSH (if required to confirm postmenopausal status, see Section 10.4) Parasitic Screening (only required in regions with high-risk or for participants who have visited high-risk regions in the past 6 months). Sites should use local laboratories. If sites wish to use central laboratories, they should note that the central test is stool microscopy for ova and parasites. For details of the organisms detected by this test refer to the parasitic screening section of the SRM. Total IgE Complement (C3 and C4) Serum samples collected at baseline will be frozen and stored for later analyses, if necessary: anti-MPO antibody, anti-PR3 antibody, ANA including anti-dsDNA antibody				

Abbreviations: ALT, alanine aminotransferase; ANA, anti-nuclear antibody; AST, aspartate aminotransferase; BUN, blood urea nitrogen; FSH, follicle-stimulating hormone; MPO, myeloperoxidase; PR3, proteinase 3; SGOT, serum glutamic-oxaloacetic transaminase; SGPT, serum glutamic-pyruvic transaminase; UACR, urinary albumin-creatinine ratio; WBC, white blood cell; WOCBP, women of childbearing potential; WONCBP, women of non-childbearing potential; GGT, Gamma-glutamyl transferase.

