- To maintain the treatment blind, the following data for post-randomization samples will not be reported to investigators and blinded Sponsor representatives: absolute and percentage values of eosinophils, neutrophils, lymphocytes, monocytes, and basophils.
- 2. Details of liver chemistry stopping criteria and required actions and follow-up assessments after liver stopping or monitoring event are given in Section 7.1.2 and Appendix 6. All events of ALT ≥3 × upper limit of normal (ULN) and total bilirubin ≥2 × ULN (>35% direct bilirubin) or ALT ≥3 × ULN and international normalized ratio(INR) >1.5, if INR measured, which may indicate severe liver injury (possible Hy's Law), must be reported to GSK as an SAE.
- 3. If alkaline phosphatase is elevated, consider fractionating.
- 4. Local urine testing will be standard for all visits (except Screening Visit and Exit Visit) unless serum testing is required by local regulation or IRB/IEC.

10.3. Appendix 3: AEs and SAEs: Definitions and Procedures for Recording, Evaluating, Follow-up, and Reporting

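### The continue-and-monitor liver table joins bilirubin and INR with *or*, so read literally it overlaps the bilirubin and INR stopping criteria

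*Protocol*

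**What the plan says.** Protocol Section 10.6.2 has two criteria rows, one for ALT 5 to <8xULN and one for ALT 3 to <5xULN. Each permits continued study intervention, with weekly monitoring, when "total bilirubin <2xULN or INR≤1.5 without symptoms believed to be related to liver injury or hypersensitivity". The Actions text includes: "Participant must return weekly for repeat liver chemistries (ALT, AST, alkaline phosphatase, total bilirubin and INR".

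The table before it, Section 10.6.1, lists the stopping events. Two matter here. One is ALT ≥3xULN with total bilirubin ≥2xULN and more than 35% direct. The other is "ALT ≥ 3xULN and INR>1.5". Either one requires immediate discontinuation. Two footnotes qualify them:

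- Bilirubin: "If serum bilirubin fractionation is not immediately available, discontinue study intervention for that participant", if ALT is ≥3xULN and total bilirubin ≥2xULN.
- INR: "the INR threshold value stated will not apply to participants receiving anticoagulants".

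Section 10.6.1 also sets follow-up intensity. When ALT is ≥3xULN with bilirubin ≥2xULN or INR >1.5, repeat tests and work-up are due within 24 hours, monitoring is twice weekly, and specialist advice is recommended. The lighter schedule (24 to 72 hours, then weekly) is for the remaining group, written as "total bilirubin <2xULN and INR ≤1.5".

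Sections 7.1.1 and 7.1.2 make discontinuation mandatory when a liver stopping criterion is met. The title of Figure 3 in Section 7.1.2 limits the monitoring algorithm to participants who meet none of them.

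**The concern.** If either of two abnormal findings is enough to stop, the group that may continue must be free of both. That needs *and*, but both rows of 10.6.2 say *or*. A participant with one marker normal and the other past its stopping threshold satisfies the monitoring row and a stopping criterion together.

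These are the cases that Appendix 6 treats as possible Hy's Law and requires to be reported as SAEs. A site working only from the 10.6.2 row could make two errors. It could give the Week 26 dose to a participant who should have stopped. It could also follow that participant weekly when 10.6.1 requires work-up within 24 hours and monitoring twice a week. The second error could occur at any time in the study. The first applies only to an event before or at Week 26, because there are only two doses (Weeks 0 and 26).

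**Working it through.** The plan gives no figure to reproduce, so the check is logical. Take one ALT row, with a participant who is asymptomatic, can be monitored weekly and has not yet met the ALT persistence criteria. The two ALT rows carry the same clause and behave alike.

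Inputs: the stopping criteria and footnotes in 10.6.1; the monitoring clause in 10.6.2; Appendix Table 1 in Section 10.2, whose chemistry panel includes "Total and directbilirubin" but does not list INR, and whose footnote says "if INR measured, which may indicate severe liver injury"; and the liver note in Section 5.2, which allows Gilbert's syndrome.

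| Bilirubin | INR | 10.6.1 | 10.6.2 as written (*or*) | Bare *and* | Proposed clause |
|---|---|---|---|---|---|
| <2xULN | ≤1.5 | no stop | monitor | monitor | monitor |
| <2xULN | >1.5, no anticoagulant | **stop** | **monitor** | excluded | excluded |
| ≥2xULN, >35% direct | ≤1.5 | **stop** | **monitor** | excluded | excluded |
| ≥2xULN, not fractionated | ≤1.5 | **stop** | **monitor** | excluded | excluded |
| ≥2xULN, >35% direct | >1.5, no anticoagulant | stop | excluded | excluded | excluded |
| ≥2xULN, ≤35% direct | ≤1.5 | no stop | monitor | excluded | monitor |
| <2xULN | >1.5, on anticoagulant | no stop | monitor | excluded | monitor |
| ≥2xULN, ≤35% direct | >1.5, on anticoagulant | no stop | excluded | excluded | monitor |
| <2xULN | not measured | no stop shown | monitor | undecided | monitor |

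Three things follow.

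1. **The overlap is real for both markers.** The bold rows meet a stopping criterion and the monitoring clause at once. Where INR is measured and the participant is not on an anticoagulant, the *or* clause excludes a stopping case only when both markers are abnormal. The non-fractionated row should be uncommon, because the central panel reports direct bilirubin.
2. **A bare *and* removes the overlap but creates gaps.** It drops participants whom 10.6.1 does not stop: those with ≤35% direct bilirubin, such as in Gilbert's syndrome, and those whose INR is raised by an anticoagulant. It also leaves the row undecided when INR has not been measured.
3. **Pointing the row at 10.6.1 does both jobs.** A clause requiring that no stopping criterion is met, footnotes included, has no overlap with stopping and keeps every non-stopping participant in the table. An unmeasured INR needs no added step, because the weekly repeats in 10.6.2 already include INR. If it comes back above 1.5 and no anticoagulant is in use, the participant meets the stopping criterion.

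The table lists logical combinations. How many overlap depends on how finely the states are divided, so the count does not measure how often the conflict would arise.

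**The case against.** The strongest reply is that the protocol already settles the matter. Discontinuation is mandatory under Sections 7.1.1 and 7.1.2. The Figure 3 title confines monitoring to participants with no stopping event. Section 10.6.1 words the complementary group correctly, and restart is not allowed. For an error to reach a participant, a site would have to apply one row of 10.6.2 and ignore the table before it. The error would then have to survive SAE reporting of possible Hy's Law cases within 24 hours, a discussion of participant safety that the surviving Actions text mentions, and weekly repeat tests. Symptomatic cases, jaundice included, are already outside the row. The INR part of the overlap also needs a test that is not in the routine panel.

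Nearly all of this stands, and it is why the severity is low. It does not make the wording correct. The notes under Figures 2 and 3 send sites to the appendix, which is where the faulty clause sits, and the criteria cell of 10.6.2 does not repeat the limit in the Figure 3 title.

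A reader might infer that the protocol tells sites to keep dosing participants with possible Hy's Law. The documents do not support that, because the mandatory stopping text governs. A reader might also infer that INR must be made a new precondition for the Week 26 dose. Removing the overlap does not require it.

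**Conclusion.** The contradiction is genuine and its consequence is small. Both rows of 10.6.2, read literally, admit participants who meet the bilirubin or the INR stopping criterion in 10.6.1. Read as a whole, the protocol stops them. What remains is a wrong conjunction in an operative safety threshold. It can matter only where a site relies on that row alone, and then only for the Week 26 dose or for the intensity of follow-up.

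The documents give no rate for such events, and few are expected. The conclusion rests on the text of the criteria cells. Figures 2 and 3 and part of the 10.6.2 Actions cell are not in the text available for review, so nothing is claimed about them; they may contain a redirect to the stopping criteria. No endpoint, estimand, power or analysis is affected.

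**What to change.** In both rows of 10.6.2, keep the ALT range, the symptom condition and the weekly-monitoring condition. Replace the bilirubin/INR clause with: *and who do not meet any liver stopping criterion in 10.6.1 (including its footnotes on bilirubin fractionation and anticoagulants)*. Do not simply change *or* to *and*, for the reasons shown in the working.

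Tell sites by clarification letter. The Amendment 2 history shows that the sponsor used one in this study in April 2022. The cost is one clause in each of two table rows and the letter. No new test, visit or analysis is needed.
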